## **9.3. Statistical Analyses**

### **9.3.1. Statistical Hypotheses**

#### **9.3.1.1. Phase 1 Dose Escalation**

Phase 1 Dose Escalation will proceed following the BOIN design to determine the MTD, and/or the 2 dose levels or schedules to be tested in Phase 2. No hypothesis testing will be performed on Phase 1. The maximum sample size of the Phase 1 Dose Escalation portion is planned to be approximately 27 subjects across the 5 planned doses.

### 9.3.1.2. Phase 2 Dose Expansion

The hypothesis for the Phase 2 Dose Expansion is provided in Section 9.1.2 as part of the sample size determination.

## 9.4. Statistical Analysis Methods

Further details of the statistical analyses will be described in the Statistical Analysis Plan (SAP). The SAP will be finalized prior to database lock.

All collected data will be reported using summary tables and figures, as appropriate. Tabulations will be produced for disposition, demographic, baseline, efficacy, and safety. Summaries will be grouped by dose level in Phase 1 and expansion dose levels in Phase 2. Categorical variables will be descriptively summarized using number and percentage of subjects, with continuous variables descriptively summarized using mean, standard deviation, median, minimum, and maximum. For time to event variables, percentages of subjects experiencing the event will be presented and the median time to event will be estimated using Kaplan-Meier methodology. As appropriate, 95% confidence intervals (CIs) will be presented.

No type I error adjustments for multiple testing are planned. No hypothesis testing will be performed on secondary or exploratory endpoints.

## 9.5. Analysis of Endpoints

### 9.5.1. BOIN Design Implementation and Assessment of MTD

A BOIN design will be employed to find the MTD. The BOIN design is implemented in a simple way incorporating features of the traditional 3+3 design but is more flexible and possesses superior operating characteristics that are comparable to those of more complex model-based designs, such as the continual reassessment method (Zhou et al., 2018). Operating characteristics will be detailed in the SAP.

[figure not shown]
The target DLT rate for the MTD is  $\phi = 0.3$  and the maximum sample size is 27, using an accelerated titration design for the first 2 dose levels. DLTs are defined in Section 8.3.7, and those DLTs that occur within the first 28 days of treatment will be used for dose finding. As shown in

Figure 1, the BOIN design uses the following rule once it has moved from a cohort size of 1 to 3, optimized to minimize the probability of incorrect dose assignment, to guide dose escalation/de-escalation:

- If the observed DLT rate at the current dose is  $\leq 0.236$ , escalate the dose to the next higher dose level;

- If the observed DLT rate at the current dose is  $> 0.359$ , de-escalate the dose to the next lower dose level;
- If the above criteria are not met, remain at the current dose until a maximum of 12 subjects have been enrolled and treated at that dose level.

**Figure 1: Flowchart for Trial Conduct Using the BOIN Design**

\* DLT rate =  $\frac{\text{Total number of patients who experienced DLT at the current dose}}{\text{Total number of evaluable patients treated at the current dose}}$

For the purpose of overdose control, doses  $j$  and higher levels will be eliminated from further consideration if  $\Pr(p_j > 0.3 \mid \text{data}) > 0.95$  and at least 3 evaluable subjects have been treated at dose level  $j$ , where  $p_j$  is the true DLT rate of dose level  $j$ ,  $j = 1, \dots, 5$ . This posterior probability is evaluated based on the beta-binomial model  $y_j \mid p_j \sim \text{binomial}(p_j)$  with  $p_j \sim \text{uniform}(0, 1)$ , where  $y_j$  is the number of subjects that experience DLT at dose level  $j$ . If the lowest dose is eliminated, the SRC will decide whether to stop the study or add a lower dose level. The

probability cutoff 0.95 is chosen to be consistent with the common practice that when the target DLT rate  $\phi \leq 1/6$ , a dose with 2/3 subjects experiencing DLT is eliminated.

The above dose escalation/de-escalation/elimination rule, which will be used to conduct the trial, is equivalently shown in

Table 5.

**Table 5: Dose Escalation/De-escalation/Elimination Rule for the BOIN Design**

Actions*	The number of evaluable subjects at the current dose (cohort size n=3)											
	1	2	3	4	5	6	7	8	9	10	11	12
Escalate if # of DLT $\leq$	0	0	0	0	1	1	1	1	2	2	2	2
De-escalate if # of DLT $\geq$	1	1	2	2	2	3	3	3	4	4	4	5
Eliminate if # of DLT $\geq$	NA	NA	3	3	4	4	5	5	5	6	6	7

The steps to implement the BOIN design are described as follows:

1. All decisions to move from one dose level to another will be made by the SRC (Section 10.1.4), guided by the principles of the BOIN design.
2. Perform accelerated titration in dose cohorts 1 and 2 as follows. Treat the first subject in the cohort and escalate the dose in a one-subject-per-dose-level fashion until any of the following events is observed in the first 28 days of treatment: (i) a DLT, (ii) an existing Grade 2 condition that worsens to Grade 3; or (iii) a new Grade 2 AE. In such a case, the cohort size for the current and all subsequent cohorts will be increased to 3.
3. To assign a dose to the next cohort of subjects, the SRC will consider dose escalation/de-escalation rules presented in

### 9.5.2. Analysis of Simon 2-stage Design

The Phase 2 Dose Expansion portion of the study will consist of 2 dose cohorts. Subjects will be assigned randomly to each Phase 2 cohort, evaluating a dose or schedule chosen by the SRC based on their evaluation of safety data and any PK, pharmacodynamics, and efficacy data obtained during the Phase 1 Dose Escalation portion of the study. Approximately 32 evaluable subjects are anticipated to enroll in Phase 2, with up to 16 subjects randomly assigned each of the 2 dose cohorts. There will be 9 subjects assigned in the first stage of the Simon 2-stage design, with the remaining 7 subjects also being assigned within a dose cohort to complete the second stage of the Phase 2 Dose Expansion portion of the study.

After evaluating the first 9 subjects for efficacy (defined as a reduction in PSA levels of  $\geq 50\%$ ) in Stage 1 (including subjects who received the same dose during Phase 1 of the study), the study will be terminated if  $\leq 1$  subject responds. If the study progresses to Stage 2, an additional 7 subjects will be treated, for a total of up to 16 evaluable subjects per dose cohort. If at least 5 subjects respond out of the total 16 within a dose cohort, there will be demonstration of efficacy of ONCT-534 within the population for this dose cohort and the corresponding null hypothesis will be rejected. Additional subjects may be enrolled to account for unevaluable subjects.

Randomized dose assignment will proceed when both cohorts are open for enrollment. If one of the dose levels is closed due to safety findings or lack of efficacy, or is paused until Stage 1 efficacy is observed, non-randomized assignments may proceed within the open dose level expansion cohort.

The expected maximum sample size in Phase 2 is 32.

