#### **4.1.3. Phase 1 Intra-Patient Dose Escalation**

Phase 1 subjects who have advanced beyond their DLT evaluation window will be offered the opportunity to escalate to a subsequent dose level that has been deemed safe by the SRC. Once the SRC has chosen the two doses for the Phase 2 expansion, Phase 1 subjects continuing treatment will be offered the opportunity to be randomly assigned to one of these Phase 2 doses, if considered appropriate by the Investigator. Subjects must have demonstrated compliance as well as a safe and favorable toxicity profile to participate in intra-patient dose escalation.

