## **9. STATISTICS**

### **9.1. Sample Size Determination**

#### **9.1.1. Phase 1 Dose Escalation**

In the Phase 1 portion of the study, 5 dose levels are planned to be evaluated in a dose escalation/de-escalation manner using a BOIN design to determine the MTD. The target DLT rate for the MTD is  $\phi = 0.3$  and the maximum sample size is approximately 27 across the 5 planned dose levels, with a maximum of 12 subjects treated per dose level.

The first 2 dose levels will use an accelerated titration design with a cohort size of 1 and will expand to a cohort size of 3 upon the first instance of a DLT, an existing Grade 2 condition that worsens to Grade 3, or a new Grade 2 AE. When this occurs then all higher dose levels will use a cohort size of 3 and follow the escalation/de-escalation/ elimination rule described in Section 9.5.1.

The dose levels to be tested will initially be 40, 80, 160, 300, and 600 mg orally once per day. Additional dose levels (e.g., intermediate levels or larger or smaller doses) or dosing schedules (e.g., twice daily) may be studied at the discretion of the SRC based on their review of safety data and any PK, pharmacodynamics, and efficacy data. If this does occur, then the number of dose levels of the BOIN design and total number of subjects included in the study will increase accordingly while using the same BOIN design for the escalation/de-escalation/elimination rules.

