### **9.1.2. Phase 2 Dose Expansion**

In the Phase 2 portion of the study, up to 16 evaluable subjects will be randomized into each of 2 expansion dose cohorts and evaluated for efficacy using a Simon 2-stage minimax design to exclude a response rate of < 10%, where response is defined as having  $\geq 50\%$  reduction in PSA. The hypothesized response rate under treatment is  $\geq 40\%$  and will be evaluated using a one-sided type I error rate of 0.025 with 80% power. A total of 9 subjects per dose level will be randomly assigned in Stage 1. If at least 2 responses of  $\geq 50\%$  reduction in PSA are observed, the dose level will proceed to Stage 2. If at least 5 responses are observed in a total of 16 subjects per dose level, the null hypothesis will be rejected.

Randomized dose assignment will proceed when both cohorts are open for enrollment. If one of the dose levels is closed due to safety findings or lack of efficacy findings, or is paused until Stage 1 efficacy is observed, non-randomized assignments may proceed within the open dose level expansion cohort. This hypothesis will require a dose cohort total of 16 for a Phase 2 Dose Expansion study total of 32 subjects.

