## **9.2. Populations for Analysis**

The DLT-evaluable Population is defined as all subjects in the Phase 1 Dose Escalation part of the study who receive ONCT-534 and either complete the 28-day DLT observation period or discontinue the study early due to a DLT. Subjects will be grouped by the dose received.

The Safety Population is defined as all subjects who receive at least one dose of ONCT-534. Subjects will be grouped by the ONCT-534 dose received at study entry.

The Efficacy-evaluable Population is defined as all subjects who receive ONCT-534 and complete at least one post-treatment disease assessment and do not discontinue due to clinical evidence of disease progression without documentation prior to obtaining post-treatment disease assessment. Subjects will be grouped by dose received.

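### Section 9.5.2 counts Phase 1 subjects at the same dose in Simon Stage 1, while Section 9.1.2 and the synopsis describe randomly assigned subjects; the plan needs one population for the gate and the final test

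*Combined protocol and SAP*

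**What the plan says.** - **Section 9.1.2**, with the same sentence in the synopsis: "A total of 9 subjects per dose level will be randomly assigned in Stage 1". A dose level goes on with at least 2 responses in 9, and the null hypothesis is rejected with at least 5 in 16. On the total: "This hypothesis will require a dose cohort total of 16 for a Phase 2 Dose Expansion study total of 32 subjects".
- **Section 9.5.2, first paragraph**: random assignment to each cohort, "with up to 16 subjects randomly assigned each of the 2 dose cohorts".
- **Section 9.5.2, second paragraph**: the first 9 are evaluated "in Stage 1 (including subjects who received the same dose during Phase 1 of the study), the study will be terminated" if no more than one responds; otherwise "an additional 7 subjects will be treated, for a total of up to 16 evaluable subjects per dose cohort".
- **Section 9.1.1**: Phase 1 runs "with a maximum of 12 subjects treated per dose level".
- **Section 4.1.3**: "Phase 1 subjects who have advanced beyond their DLT evaluation window will be offered the opportunity to escalate to a subsequent dose level". Phase 1 subjects still on treatment may also be randomly assigned to one of the Phase 2 doses.
- **Section 9.2**, efficacy-evaluable population: "Subjects will be grouped by dose received". The safety population is grouped by the dose at study entry.
- **Sections 4.1.2 and 9.5.2**: the Safety Review Committee (SRC) picks the two Phase 2 doses from Phase 1 safety data and any PK, pharmacodynamic and efficacy data.

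**The concern.** Phase 1 subjects receive their dose through BOIN escalation, not randomization. The only stated departure from random assignment applies when one Phase 2 cohort is closed or paused, and it concerns enrollment into the open cohort. It does not cover Phase 1 subjects. The plan therefore holds two definitions of the nine subjects at the gate, and of the sixteen in the final test.

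The difference can change a decision. Suppose 2 of 3 Phase 1 subjects at a dose respond, then none of the first 6 and 1 of the first 9 new subjects. The second paragraph of Section 9.5.2 counts 2 of 9 and continues. Section 9.1.2 counts 1 of 9 and does not. If the reading is settled after results are known, that choice can decide whether a dose proceeds.

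Three further points follow from the same text:

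- After intra-patient escalation one subject may have received two doses, so it is not clear for which dose he counts.
- If Phase 1 PSA responses help to choose a dose and are then counted in its test, the same responses are used twice.
- The stopping sentence in Section 9.5.2 speaks of the study. Section 9.1.2 applies the gate to each dose level.

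**Working it through.** **Inputs.** From Section 9.1.2: null rate 0.10, alternative 0.40, one-sided 0.025, power 80%, at least 2 of 9 to continue, at least 5 of 16 to reject, total 32. From Section 9.1.1: at most 12 Phase 1 subjects per dose. The number carried in per dose, m, is not in the plan; 3, 6 and 9 are shown.

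**1. The plan's own design.** P(reject) = Σ over x = 2 to 9 of P(X1 = x; 9, p) × P(X2 ≥ 5 − x; 7, p).

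- At p = 0.10: 0.17219 × 0.02569 + 0.04464 × 0.14969 + 0.00744 × 0.52170 + 0.00089 (x ≥ 5) = 0.0159.
- At p = 0.40: 0.0935 + 0.2110 + 0.2438 + 0.2666 (x ≥ 5) = 0.8149.

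Both meet the stated limits, and an exhaustive search returns this design as the minimax solution. The Simon figures are right.

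**2. New subjects needed with carry-in.** Per dose 16 − m, over two doses 2 × (16 − m). For m = 3, 6, 9 this is 26, 20 and 14, against 32. Because 12 per dose are allowed in Phase 1, m = 9 is possible.

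**3. How often the gate decisions differ.** Both readings share the first 9 − m new subjects. Section 9.5.2 adds m Phase 1 subjects; Section 9.1.2 adds the next m new ones. With x responders among the shared subjects, each reading stops with probability q(x) = P(Bin(m, p) ≤ 1 − x). With two or more shared responders both continue. So P(differ) = Σ over x = 0, 1 of P(x) × 2 × q(x) × [1 − q(x)].

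- m = 3, p = 0.10: 0.5314 × 2 × 0.9720 × 0.0280 + 0.3543 × 2 × 0.7290 × 0.2710 = 0.0289 + 0.1400 = 0.169.
- m = 9, p = 0.10: 2 × 0.7748 × 0.2252 = 0.349.

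| True rate | m = 3 | m = 6 | m = 9 |
|---|---|---|---|
| 10% | 17% | 27% | 35% |
| 20% | 25% | 38% | 49% |
| 40% | 8% | 12% | 13% |

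The formula is symmetric: half of each figure is Section 9.5.2 continuing where Section 9.1.2 would stop (8%, 13%, 17% at a true rate of 10%), and half is the reverse. In the first half both counts come to be observed for m = 3 or 6, since 13 or 10 new subjects are enrolled. At m = 9 only 7 are, two short of the nine. In the second half Section 9.5.2 stops before the last m new subjects are enrolled, so the issue is whether to stop or enroll on.

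**4. Error rate at p = 0.10.** Let y be the responders among m carried in. For m = 3 and y = 0, 1, 2, 3 the probability of rejection is 0.0054, 0.0327, 0.1339 and 0.3787. Weighted by the chance of each y: 0.729 × 0.0054 + 0.243 × 0.0327 + 0.027 × 0.1339 + 0.001 × 0.3787 = 0.0159. Carry-in alone changes nothing. The rate moves only if doses with higher y are more likely to be chosen.

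**5. Illustrative simulation.** Table 5 with one-subject titration at the first two doses, cap 27, 12 per dose. Five assumed DLT curves, from (.01, .01, .02, .03, .05) to (.08, .15, .30, .45, .60), with the probability of a titration-ending Grade 2 event set at 0, 0.5 or 1. The PSA response rate is 10% at every dose.

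- MTD and next lower dose, PSA not used: 6.2–7.0 carried in per dose on average, about 18–20 new subjects, error 1.6%.
- MTD fixed, PSA picks the other dose: 1.8–3.8% for the picked dose, 1.7–2.7% averaged over both.
- Doses ranked on PSA response alone, which is not the documented process: 3.1–4.6% for the top dose, 1.8–3.1% on average.

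In the two PSA-based cases, runs with fewer than two candidate doses (0–48%) were left out.

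**The case against.** The strongest reply is that the parenthesis in Section 9.5.2 is explicit, gives a usable count on its own, and reflects an acceptable wish to treat fewer new subjects. That stands as an argument for keeping carry-in. It does not remove the conflict: the first paragraph of the same section disagrees, and nothing says that Section 9.5.2 overrides Section 9.1.2. Section 9.4 leaves detail to a SAP due before database lock, which need not precede the Stage 1 gate.

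Four further points stand and limit the concern.

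- **The gate percentages are not harm.** A reader might take them as bias. They are chance differences between partly or wholly different samples; at m = 9 they are simply two independent samples of nine disagreeing.
- **A reader might infer that carry-in breaks the 2.5% error rate.** The documents do not support that. They allow efficacy data as one input to dose choice but do not say that PSA drives it. The exact rate of 1.6% leaves room, and some cases with PSA-based selection stay below 2.5%.
- **Fourteen new subjects is an extreme.** It needs at least 9 Phase 1 subjects at both chosen doses, which occurred in about 1–22% of simulated runs. Several sample-size statements are also ceilings or approximations; only the total in Section 9.1.2 is worded as a requirement.
- **The bare wording on dose received is not peculiar to efficacy.** The DLT-evaluable population uses it too. The ambiguity after escalation under Section 4.1.3 remains.

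**Conclusion.** The inconsistency is real and should be fixed before Phase 2 opens. Two populations are described for the 2-of-9 gate and the 5-of-16 test, and no other section resolves them. Depending on how many Phase 1 subjects are carried in (3 to 9), the gate decision differs between readings in 17–35% of cases at a true rate of 10% and in 8–13% at 40%. These figures are exact, assume no dose selection on PSA and a common response rate in both phases, and carry no direction.

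The error rate is 1.6% per dose if Phase 1 PSA response did not influence dose choice. If it did, the 2.5% ceiling may or may not hold; it is not guaranteed. The simulated ranges rest on assumed toxicity curves and selection rules and show only the order of size. The Simon design itself is correct.

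**What to change.** Make Section 9.5.2, Section 9.1.2 and the synopsis name one population for Stage 1 and the final test. Either option works, and the choice is the sponsor's.

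- **(a) New subjects only.** Count only subjects newly enrolled in Phase 2, say that Phase 1 subjects escalated or re-assigned under Section 4.1.3 do not count, and summarize Phase 1 subjects at the same dose separately. Cost: up to 9 more newly treated subjects per dose, 18 in total, than the second paragraph of Section 9.5.2 implies (about 12–14 on average in the simulation), all within the stated 32.
- **(b) Keep carry-in.** Say so in Section 9.1.2 and the synopsis. Define how many and which Phase 1 subjects count, and whether the same dose means the dose at study entry. Restate 32 as including carried-in subjects. State that the 2.5% error rate is not guaranteed if their PSA response influenced dose selection. Cost: wording only, no added subjects, but an error rate that depends on how the doses were chosen.

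Under either option, reconcile the stopping sentence in Section 9.5.2 with the gate that Section 9.1.2 applies to each dose level.

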## 7.2. Subject Replacement

The BOIN design does not require that subjects in the Phase 1 portion of the study who are not DLT evaluable (as defined in Section 9.2) be replaced unless the cohort size is one. Subjects who receive ONCT-534 and withdraw prior to Day 28 due to a DLT will not be replaced, and subjects who are not evaluable may be replaced at the discretion of the Sponsor and SRC.

Subjects in the Phase 2 portion of the study may be replaced, after discussing with the Sponsor, if they are not evaluable for efficacy (as defined in Section 9.2) for the purpose of estimating clinical activity of ONCT-534 and discontinued the study for reasons not related to study drug or disease progression.

Additional subjects may be enrolled beyond the planned sample size to provide sufficient data for analysis of safety, efficacy, PK and/or pharmacodynamics.

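### Sections 7.2 and 9.5.2 do not give the same replacement rule for Phase 2, so early treatment failures can be replaced in the Simon PSA50 test

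*Combined protocol and SAP*

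**What the plan says.** Section 9.1.2 sets up the test in each dose cohort: "up to 16 evaluable subjects will be randomized into each of 2 expansion dose cohorts". The aim is to "exclude a response rate of < 10%, where response is defined as having" a PSA reduction of at least 50%. The target rate is 40% or more, and the design is to be "evaluated using a one-sided type I error rate of 0.025 with 80% power". On numbers, "A total of 9 subjects per dose level will be randomly assigned in Stage 1". Two responses open Stage 2, and five among 16 reject the null.

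Three sections bear on who fills those slots:

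- **Section 7.2** lets a Phase 2 subject be replaced, after discussion with the sponsor, if two things hold: he is not evaluable for efficacy as defined in 9.2, and he "discontinued the study for reasons not related to study drug or disease progression". Its last paragraph separately allows enrolment beyond the planned size to obtain enough data, including efficacy data.
- **Section 9.5.2** counts evaluable subjects up to 16 per cohort and adds: "Additional subjects may be enrolled to account for unevaluable subjects".
- **Section 9.2** requires at least one post-treatment disease assessment for efficacy evaluability, and that subjects "do not discontinue due to clinical evidence of disease progression without documentation prior to obtaining post-treatment disease assessment".

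Table 1 schedules PSA at Weeks 4 and 8, and both PSA and the first on-treatment scans at Week 12.

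**The concern.** Under 7.2, a subject who stops early for drug toxicity or progression is not replaceable. Under 9.5.2 taken alone, he can be, because he may be unevaluable and no reason is asked for. Section 9.2 expressly makes unevaluable those who stop for undocumented clinical progression before an assessment. It does the same for anyone with no post-treatment disease assessment, and scans start only at Week 12.

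These men are unlikely to be PSA50 responders. Replacing them removes failures from the 9 and the 16 and raises the response rate among those who remain. The Simon rule is the only formal efficacy test in the plan, and with a Stage 1 threshold of two responses in nine, a single substitution can change whether a dose goes on.

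Applying 7.2 strictly would still leave a gap. No section says that an early failure who is not replaced stays among the 9 and 16, or that he counts as a non-responder.

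**Working it through.** **Inputs from Sections 9.1.2 and 9.5.2.** Null rate 10%, target rate 40%, n1 = 9, continue at 2 or more, n = 16, reject at 5 or more, one-sided 0.025, power 80%.

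**Input not in the documents.** The share u of treated subjects who are non-responders, become unevaluable and are replaced. Assumed range: 0 to 30%.

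**Step 1: reproduce the plan's design.** With response rate p in the subjects who fill the slots,

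P(reject) = Σ (x = 2 to 9) C(9,x) p^x (1−p)^(9−x) × P[Bin(7,p) ≥ 5 − x].

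At p = 0.10 the terms are:

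| Stage 1 responses x | P(x of 9) | P(enough in the next 7) | Product |
|---|---|---|---|
| 2 | 0.17219 | 0.02569 | 0.00442 |
| 3 | 0.04464 | 0.14969 | 0.00668 |
| 4 | 0.00744 | 0.52170 | 0.00388 |
| 5 or more | about 0.0009 | 1 | about 0.0009 |

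The sum is 0.0159. At p = 0.40 the same formula gives 0.815. The chance of stopping after Stage 1 under the null is 0.775. A search over two-stage designs with alpha at most 0.025 and power at least 0.80 returns this same minimax design, so the plan's figures reproduce. The exact type I error is 1.59%, which leaves slack below 2.5%.

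**Step 2: null defined in evaluable subjects.** The slots are filled by subjects with rate 10% whatever the share replaced. Type I error stays at 1.59%.

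**Step 3: null defined in all treated subjects.** If the treated rate is 10% and a share u, all non-responders, is replaced until 9 and then 16 evaluable subjects are reached, the rate among slot-holders is 0.10/(1 − u). Putting that into the Step 1 formula:

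| u | 0.10/(1 − u) | Type I error |
|---|---|---|
| 0 | 0.1000 | 1.59% |
| 5% | 0.1053 | 1.95% |
| 10% | 0.1111 | 2.42% |
| 15% | 0.1176 | 3.02% |
| 20% | 0.1250 | 3.81% |
| 25% | 0.1333 | 4.85% |
| 30% | 0.1429 | 6.24% |

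The 2.5% level is reached at a slot-holder rate of 0.1121, that is u = 1 − 0.10/0.1121, about 10.8%. In head-count terms, two replaced among 18 treated (u = 2/18 = 11.1%) gives 2.54%; one among 17 gives 2.03%. Simulation with 200,000 runs per setting agrees: 2.41%, 3.80% and 6.25% at u = 10%, 20% and 30%.

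**Step 4: early failures kept as non-responders.** With a treated rate of 10% and no replacement of these subjects, type I error returns to 1.59%. If 40% was the rate among evaluable subjects only, the treated rate under the alternative is 0.40 × (1 − u), and power is 77.0% at u = 5%, 71.8% at 10% and 59.7% at 20%.

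**The case against.** A reader might infer that the plan breaches its own 2.5% error rate. The documents do not support that. Sections 9.1.2 and 9.5.2 place the test in evaluable subjects, and in that population type I error is 1.59% however many are replaced. The excess needs the 10% null to be a rate for all treated subjects, which no section states, and a value of u above about 11%, which no section gives. Replacement is also optional, entry requires a life expectancy of at least 6 months, and Section 8.1.12 asks for every effort to document progression after stopping. All of this stands.

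A reader might also infer that 7.2 and 9.5.2 flatly contradict each other. That is too strong. Section 9.5.2 does not say that every unevaluable subject may be made up whatever the reason, and a general permission can be read as subject to the dedicated rule in 7.2. But 9.5.2 does not say that it is, and the closing paragraph of 7.2 opens a further route to extra enrolment for efficacy data.

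Thirdly, 9.5.2 defines efficacy by PSA and does not name the efficacy-evaluable population. A man with PSA values at Weeks 4 and 8 but no scan might therefore count as evaluable for this test. Against that, 7.2 ties evaluability for efficacy to 9.2, the synopsis describes disease assessments as CT and bone scans, and 8.1.1.4 lists disease assessment and PSA separately. The text is unclear. Even if PSA counted, stops before Week 4 and the undocumented-progression exclusion would remain.

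Finally, Section 9.4 leaves further detail to an SAP. It need only be final before database lock, which can be after the replacement decisions have been taken.

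**Conclusion.** The two replacement rules are not aligned. As written, 9.5.2 allows early treatment failures to be replaced in the trial's one formal efficacy test, and no section says how such subjects count if they are not replaced. This is a selection problem and an unsettled target population, not a demonstrated breach of the error rate.

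Its size depends on two things that the documents leave open. With a null in evaluable subjects, type I error is 1.59%, but the result does not describe everyone treated. With a null in all treated subjects, it ranges from 1.59% at u = 0 to 6.2% at u = 30% and passes 2.5% at about 11%, on the assumption that every replaced subject is a non-responder. It should be settled before Phase 2 subjects are replaced.

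**What to change.** In 9.1.2 and 9.5.2:

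1. Make additional enrolment for unevaluable subjects subject to both conditions of 7.2, by explicit reference.
2. State that the last paragraph of 7.2, on enrolment beyond the planned size, does not change who fills the 9 and 16 Simon slots.
3. State that a treated subject who stops for study-drug toxicity or disease progression keeps his slot and counts as a PSA50 non-responder, unless a qualifying PSA decline was already recorded.
4. State that a subject with post-baseline PSA values counts on those values, whether or not a scan was done.
5. Say whether the 10% and 40% refer to treated or evaluable subjects.

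This costs a few sentences, and the planned 16 per cohort can stand. If the 40% was meant for evaluable subjects only, power for treated subjects is below the stated 80%: about 72% at u = 10% and 60% at u = 20%. The plan should then say so; restoring 80% would need more subjects.
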